5.6 Identification of the subject

Study subjects will be identified by a number and the initials of their name.

The initials of the study subject will be obtained starting with the first letter of the name, followed by the first letter of the first surname and the first letter of the second surname, obtaining a maximum of three letters, in case the person has two names or compound surname, the first letter will always be used.

Example:

A) [name]
to. Initials: AMC

[figure not shown]
B) [name]
b. Initials: JDO

In the counting stage, the participant number will be assigned consecutively, using 3 consecutive digits.

Once the subject has been selected, they will be assigned a number with which they will be identified throughout the study. This code will be made up of eight numbers in the following order from left to right:

- three digits of the molecule under study according to the name by the sponsor.
- Two digits correspond to the research center number.
- three digits of the number following their inclusion assigned in the research center.

Example of assigned number:

6. Investigational product and treatment

6.1 Managed Products

6.1.1 Investigational product

- PRO-201 . Atropine Sulfate 0.01% Ophthalmic solution. Zapopan, Jalisco, Mexico. Laboratorios Sophia, S.A. de C.V
- Route of administration: Ophthalmic.

6.1.2 Investigational Product Dosage

- Dosage: 1 drop once a day (QD) in the evening, in both eyes (AO).

6.1.3 Treatment with the investigational product

The investigational product will be delivered at the conclusion of the baseline visit, and the investigational subject will administer the drops at night, applying a total of one drop at night to each eye during the 14 days of application.

The baseline visits and visit 1 should be done in the morning shift, before 4:00 p.m., so that the patient can have enough time to apply PRO-201 at the indicated time.

6.2 Storage and handling of the investigational product in the study center

The delivery will be made by means of a courier service contracted by the sponsor, expressly selected for this purpose, to the address of the research center according to the study plan.

The reception will be carried out by the assigned personnel of the research team. You will need to check that the primary packaging (box) is in good condition. If you show alterations or defects in its integrity that in your judgment could have damaged the content, you must report it to the sponsor. If the package does not show significant defects, it will proceed to open it.

Inside the shipment you must locate the acknowledgment document and the temperature meter (*data logger*). You must check that the temperature recorded complies with what is specified for transport and safekeeping. It will verify the content (PI) with what is reported in the document. In case the document corresponds to the content, you will sign the receipt and send it to the sponsor. Otherwise, it will notify the sponsor.

Storage and safeguarding are the responsibility of the research center. The medication must be stored in a secure area with restricted access.

The storage temperature should be between 2° and 30°C.

From its receipt at the center and until there is no stock of PI stored, the research center has the obligation to review the storage conditions of the PI daily and manually record, in the designated

format, the temperature set by the *data logger* (current, minimum and maximum temperature). Such data will be reviewed by the clinical monitor during their monitoring visits according to the records stored in the *data logger's memory*.

In the event of loss of material, it must be documented in the logbook of inputs and outputs along with a clear description of the mechanism by which the loss occurred.

Upon completion of the protocol, all study material will be retrieved by the sponsor as part of the closing visit. The final delivery of materials will be made by the principal investigator or the person designated by him to deliver material at the end of the study.

The sponsor reserves the right to initiate civil and criminal action against the principal investigator in the event of a lack of undocumented material at the conclusion of the study.

6.3 Concomitant treatments and medications (permitted and prohibited)

Any medication that is used, in addition to appearing in the clinical note, must be registered in the concomitant medications section of the eCRF.

Allowed medications:

- Ophthalmic:

All permitted medications applied via ophthalmic medication during the study must wait a minimum period of 10 minutes from the last application of the treatments under study or reference. The above is to avoid the interaction of treatments in the tear film, based on the flow index and physiological tear volume. [26]

- o Tetracaine 0.5%
- o Tropicamide 0.8% /Phenylephrine 5%
- o Hypromellose 2%
- o Fluorescein
- o Lysmine Green

Prohibited Medications:

- Any ophthalmic medications that are not on the list of allowed medications
- Any systemic medication

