5.5 Procedure in case of early discontinuation

For this protocol, early discontinuation is defined as those subjects who were assigned to the PI, who at some points were active subjects of the study, but their final evaluation could not be completed.

If the subject does not terminate their participation due to withdrawal of consent or major deviation, the last visit, in which their withdrawal was determined, will be considered their final visit. Subjects who are removed due to the presence of AEs will continue with the follow-up that is defined until the closure of their AE.

In cases where the participating subject does not attend their appointment, the research center must make a call to find out the reason and will try to make a new appointment within the established window period or an unscheduled appointment. If it is not possible to make an appointment, the subject will be considered as loss of follow-up and will be asked about the presence of adverse events and the reason for leaving the study, as minimum data.

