8.4 Definitions relevant to the classification of adverse events

Severity (serious/non-serious), also called seriousness (serious/non-serious). Serious or serious is defined as any event that: results in death, threatens life, requires hospitalization or prolongs hospitalization, is a cause of permanent or significant disability or disability, is the cause of alterations or malformations in the newborn, other medically important conditions.

Severity (mild, moderate, or severe). Mild is those that present with minimal symptoms, do not require treatment or suspension of the medication; moderate, when they interfere with usual

activities, without threatening the subject's life, require treatment and may or may not require discontinuation of the medication; severe, those that interfere with usual activities and require pharmacological treatment and discontinuation of the medication. [36][47][48]

Causality. It is the relationship that is assigned between the pharmaceutical product and the adverse event: certainly caused by the pharmaceutical product, there is clear evidence of causality, i.e. the adverse event reappears with the administration of the pharmaceutical product; probably caused by the pharmaceutical product, there is a high suspicion of causality but no direct evidence is available or it is considered unnecessary or dangerous, i.e. the reaction disappears when the pharmaceutical product is discontinued; possibly caused by the pharmaceutical, there is additional information to suggest that the cause may be due to another pharmaceuticals or disease; unlikely to be caused by the pharmaceutical product, there is a clear explanation of the origin due to the underlying disease or the use of another pharmaceutical product; conditional, there is a lack of data to issue a clear causality; non-classifiable, those for which once all possible information has been obtained about the adverse event, it remains unclassifiable. [36] [47] [48] [49]

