8.5 Responsibilities of the researcher

It is the responsibility of the Investigator to verify AEs through questioning, pertinent physical examination, assessment of evolution, as well as appropriate medical and pharmacological management; as well as to follow up until the resolution or outcome and definitive discharge of the AE, following the definitions determined in national and international regulations. [36] [47] [48]

In the event of an AE or any event that puts the health and well-being of the subjects at risk, pertinent medical care will be provided, either at the research center or will be referred to the Hospital Center with the highest resolution power with which the research center has a medical care agreement. The PI will notify the sponsor's clinical monitor, according to the times established in national and international regulations. In the case of serious adverse events, it will notify the sponsor and record the corresponding information in the eCRF and in turn, inform the IRB and IC.

The attention of the AEs will be carried out according to the event care diagram (see Figure 4. Adverse Event Care).

The sponsor's final report will include the report of adverse events in compliance with current national and international regulations. [36] [47]

If the research subject debuts during their participation in the study with any chronic adverse event, such as diabetes or systemic arterial hypertension, they will be referred to the competent health professional for chronic treatment. The follow-up and termination of your participation will be in accordance with the stipulations of the ICH.

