4. Taking the clinical information collected, either during the care provided at the research center or that provided by the treating physician(s) in the hospital, the PI will record the AE in its clinical note, stating the seriousness, intensity (mild, moderate or severe) and relationship with the investigational product.
5. The PI must migrate the relevant data to the eCRF and its respective adverse event section. By, in cases of serious adverse events, the clinical monitor of the study must be notified within 24 hours after learning it, so that in turn it informs the Clinical Team and the UTFLS, and that the CEI/CI is subsequently notified. Non-serious adverse events will be recorded and treated appropriately, and the safety profile of the investigational drug or PI will be reported to the appropriate regulatory entity in the final report of the clinical trial.

The recording of the outcome of the AE depends substantially on the follow-up that the Principal Investigator performs on the subject, since it is expected that most of the harmful phenomena (see subsection 2.5 Risk-benefit assessment and consult the Investigator's Manual) are ophthalmic in nature, however, there may be systemic alterations. Therefore, in the opinion of the researcher, the withdrawal of the participant or their permanence will be considered.

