10.3.3 Exploratory Analysis

The analysis of exploratory variables will be carried out in those subjects who conclude their participation without deviations from the study protocol (population by protocol, PP). The same primary analysis will be carried out if they have the necessary measurements to do so.

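### Section 6.3 bans every unlisted drug while 8.5 and 8.5.3 require adverse events to be treated; read literally, subjects treated for an adverse event leave the exploratory safety analyses

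*Combined protocol and SAP*

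**What the plan says.** Section 6.3 lists five permitted ophthalmic agents: tetracaine, tropicamide/phenylephrine, hypromellose, fluorescein and lissamine green. Sections 7.4.5.8, 7.5.8.6 and 7.5.9 describe their use as examination aids. The section then prohibits "Any ophthalmic medications that are not on the list of allowed medications" and "Any systemic medication". It states no exception for treating an AE. It also says "Any medication that is used, in addition to appearing in the clinical note, must be registered in the concomitant medications section of the eCRF", which is a rule about recording and does not permit use.

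Section 8.5 lists among the investigator's responsibilities the verification of AEs, "as well as appropriate medical and pharmacological management". Section 8.5.3 says "Non-serious adverse events will be recorded and treated appropriately".

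For the analysis, section 10.3.3 restricts the exploratory variables to "those subjects who conclude their participation without deviations from the study protocol". It draws no line between minor and major deviations. Section 10.3.2.1 places safety and tolerability outcomes in all subjects with at least one dose, whatever their adherence to the protocol, and 10.3.2.2 applies the same analysis to the secondary variables.

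**The concern.** A site cannot always obey both parts of the protocol. Headache, dry eye and ocular allergic reactions are on the list of expected events in 2.4.1 and 7.4.5.9, so drug treatment of an AE is foreseeable. When it happens, section 8 has been followed and section 6.3 has been breached.

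The breach matters because of the any-deviation rule in 10.3.3. The variables analysed under that rule are not peripheral: section 3.1.2.3 names distance acuity, intraocular pressure, staining and vital signs as safety measures and the comfort index as a tolerability measure. A subject would leave these analyses because an AE occurred and was treated. Exclusion of that kind is informative: the subjects removed are more likely to have had a worse experience on the product.

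**Working it through.** **Step 1. The passages side by side.**

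| Topic | Section 6.3 | Section 8 |
|---|---|---|
| Eye drops other than the five agents | Prohibited, no exception | Pharmacological management of AEs is the investigator's responsibility (8.5) |
| Systemic drugs | Prohibited, no exception | Non-serious AEs are to be treated (8.5.3); the AE record covers drugs used for a passing sign or symptom (8.5.1) |

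No passage reconciles the two. The same gap appears elsewhere: 5.1.1 accepts hormonal contraception as one way to meet the contraception requirement, although 6.3 bans systemic medication without exception.

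**Step 2. Which analyses are reached.**

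- Primary variables (unexpected related AEs, photophobia): all dosed subjects (10.3.2.1). Loss by this route: 0.
- Secondary variables (pupillary diameter, expected related AEs, near acuity): same analysis (10.3.2.2). Loss by this route: 0.
- Exploratory variables (distance acuity, intraocular pressure, staining, vital signs, comfort index): subjects without deviations only (10.3.3). Loss: every subject given an unlisted drug for an AE.
- Elimination from the study: use of a prohibited drug is not among the five criteria in 5.2.1.

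**Step 3. Size.** The planned number reproduces from section 10.1.2: 24 × 1.20 = 28.8, rounded up to 29. This checks only the inflation step, and the present point does not change the 29.

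The documents give no rate of drug-treated AEs, so let *q* be the assumed proportion of subjects given an unlisted drug for an AE. With 29 subjects, the expected loss is 29 × *q*, and the chance of losing at least one is 1 − (1 − *q*)^29.

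| Assumed *q* | Expected loss | Chance of at least one |
|---|---|---|
| 2% | 29 × 0.02 = 0.6 | 1 − 0.98^29 = 44% |
| 5% | 29 × 0.05 = 1.5 | 1 − 0.95^29 = 77% |
| 10% | 29 × 0.10 = 2.9 | 1 − 0.90^29 = 95% |

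**Step 4. Effect on the results.** Suppose the excluded subjects' mean change is worse than that of the others by *d*. The mean over everyone is the others' mean plus *q* × *d*; the mean after exclusion is the others' mean alone. The reported mean is therefore too favourable by *q* × *d*, that is, by 2% to 10% of *d* over the range above. The documents give no value for *d*. Section 10.3.1 also reports the maximum and minimum, and there a single exclusion can remove the worst value.

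**The case against.** The strongest reply is that this is a wording gap with little reach. Both primary thresholds and all secondary variables use every dosed subject. Leaving out subjects who took another eye drop is a recognised per-protocol choice for staining or comfort, since the drop may itself change the value. Large changes would still be seen: sections 7.4.5.1, 7.4.5.6 and 7.4.5.8 make set limits for pressure, acuity loss and staining reportable as AEs. Much of the recording also exists already, because 6.3 and 8.5.1 capture the drug, dose, route, dates and reason.

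Most of this stands and limits the point. It does not remove it. The contradiction between 6.3 and section 8 remains, the deviation status of AE treatment is not stated anywhere, and safety measures would be summarised only in a set that sheds subjects treated for AEs.

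A reader might infer more than the documents support:

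- **That severity grading is distorted.** Section 8.4 describes moderate events as those that interfere with usual activities and "require treatment and may or may not require discontinuation of the medication"; severe events also involve discontinuation. The grade depends on what the event needs, not on whether a drug was given, so the ban does not change a correctly applied grade.
- **That AE follow-up is cut short.** Section 5.5 mentions ending participation in the clause "If the subject does not terminate their participation due to withdrawal of consent or major deviation", but it does not define a major deviation or say that AE treatment is one. The same section continues follow-up of subjects removed for AEs until the event closes, and 8.5 requires follow-up to resolution or outcome.
- **That the loss could be much larger, judging by the 30% who reported burning in section 2.2.2.** That burning was mild, after one drop of a 1% product, 100 times the present concentration. By 8.4, mild events do not need treatment.

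**Conclusion.** The concern holds in a limited form. Section 6.3 contradicts 8.5 and 8.5.3, and the passages must be reconciled. Read literally together with 10.3.3, they drop subjects from the exploratory safety and tolerability results because an AE was treated, and this may make those results look more favourable. At assumed treatment rates of 2% to 10%, the expected loss is about 0.6 to 2.9 of 29 subjects. The result rests on that assumed range and on a literal reading of the any-deviation rule. The direction of the bias further assumes that treated subjects did worse on these measures, which is plausible but cannot be shown from the documents. The primary and secondary analyses, the planned 29 subjects and AE follow-up are untouched. The point should be fixed because the remedy is cheap; it does not threaten the main conclusions.

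**What to change.** Reconcile 6.3 with 8.5 and 8.5.3. Which treatments are allowed is for the sponsor to settle. Then state in 6.3 and 10.3.3 that medication given to manage an AE is recorded and flagged as AE treatment and does not by itself remove a subject from the exploratory safety analyses. As an alternative, keep the per-protocol analysis and also report the same five variables in the safety population defined in 10.3.2.1.

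The cost is a sentence in each section and one flag in the eCRF, handled through the amendment procedure in 11.2. The sample size does not change. The downside is small: some values will have been measured under AE treatment. The flag identifies them, so they can be listed separately.

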6.4 Procedure for monitoring and measuring adherence

For more than four decades, there has been a lot of research on the appropriate way to measure and quantify medication adherence, but none has reached a consensus to stand as the gold standard, both in cross-sectional and longitudinal studies. [27, 28, 29, 30, 31, 32, 33, 34]

There are different procedures to measure adherence to pharmacological interventions. The most common procedure includes self-reports, which include patient interviews, questionnaires and self-monitoring diaries. Its strengths are speed, flexibility, low cost and ease of implementation; They have a high degree of specificity for non-adherence, however, the sensitivity and reliability for adherence is low. [34, 35]

The biochemical measurement of the drug, or its metabolite, is one of the methods that best confirms the use of the drug. However, in addition to raising costs and being impractical, it is of little use in the context of ophthalmic applications, since concentrations at the peripheral level could be undetectable; and samples of other tissues involve more invasive methods that would not be advisable. [34]

There is no standardized parameter to define adequate adherence, it must be defined and delineated by the objectives of the research. [34]

For this study, a minimum adherence of 90% (per subject's diary) will be necessary to meet the objectives of the research. Therefore, subjects with adherence of less than 90% will not be considered for the evaluation of exploratory variables but will be considered for the safety and tolerability variables in the intention-to-treat population group.

6.5 Strategies to improve adherence

1. The PI will sensitize the subject to the importance, to achieve the objectives of the study, of the correct application of the concomitant treatment.
2. Direct questioning by the PI about the application of the concomitant treatment.
3. Delivery of a printed calendar specifying the date of the visit and its activities.

If deemed necessary, text messages may be sent as reminders. The content of these messages must be approved in advance by the CEI.

7. Study methods and procedures

7.1 Research center

This study will be carried out in a research center previously evaluated by the sponsor. The center will be an institution or establishment where health research is carried out that complies with current regulations.

The research center will be responsible for forming a multidisciplinary research team to execute the clinical study according to the protocol. It is their prerogative to design the organization and select the personnel who will perform the functions. However, it is necessary for the sponsor to sponsor that the PI and sub-investigator be ophthalmology specialists.

Any person who is designated, under the responsibility of the PI, as a part of the study monitoring (sub-investigator, nurse, etc.) or a specific function of participation in the study (pharmacist, administrative assistant, study coordinator, etc.) must appear in the "Delegation of Responsibilities".

The competence and training of any person who has direct participation in the activities of the study must be verified prior to the performance of any activity related to the protocol. The above must be recorded and the documents that constitute evidence of this competence and/or training must be kept in the master file of the study. The competence and training of the staff who have functions in the study, both at the central level and in the study center, is the responsibility of the sponsor.

The sponsor must ensure that all study site personnel participating in the study are adequately trained on the study (research protocol, investigator's manual, amendments, standard operating procedures, etc.) and on ICH Good Clinical Practice, prior to the start of their participation in the study. Training must be recorded in writing, and those records must be filed in the master record of the study.

7.2 Clinical Study Registration

This clinical study will be registered by the sponsor in public clinical trial registries before its start (inclusion of the first subject): National Registry of Clinical Trials (RNEC) of the Federal Commission for the Protection against Health Risks (COFEPRIS) and in a WHO primary registry platform. WHO Primary Registries meet specific criteria for content, quality and validity, accessibility, unique identification, technical capacity and administration. WHO Primary Registries meet the requirements of the International Committee of Medical Journal Editors (ICMJE).

